We are proposing a clinical study to test the hypothesis that Hyperbaric Oxygen (HBO $_2$) given in the immediate postoperative period for a total of 10 treatments after Below-the-Knee Amputation (BKA) will reduce postoperative complications. Patients scheduled for BKA at Duke University Medical Center will be reviewed for contraindications to HBO $_2$. Patients for whom HBO $_2$ is not contraindicated may choose to be enrolled in the study. Patients enrolled will be randomly assigned to receive treatment or standard postoperative care. Each patient receiving treatment will receive twice daily HBO $_2$ for 2 hours at 2 ATA. Patients receiving HBO $_2$ will breathe 100% oxygen via head tent while inside a hyperbaric chamber at Duke University Hospital. The statistical plan for this study will test non-directional hypotheses (two-sided tests). Bonferroni correction will be used to adjust for multiple tests. SAS 9.4 (SAS Institute, Inc.) will be used to analyze the data. The main analysis of the primary efficacy hypotheses will include data from all randomized patients in the group to which random assignment is made. Hence, the analysis will be intention to treat.

Research Summary

State your primary study objectives

This study will primarily aim to assess whether patients receving treatment suffered fewer complications, as defined by the Vascular Quality Initiative, vs. patients who receive standard care.

State your secondary study objectives

This study will secondarily collect data pertaining to hospital length of stay, 90-day mortality, failure to heal at 4 and 8 week follow-up visits and ability to ambulate with a prosthesis at 6 months post amputation.

Please select your research summary form:

Standard Research Summary Template

This is the regular (generic) research summary template which is required for all regular applications (unless your protocol fits under the other research summary templates in this category). Use of these instructions is helpful for ensuring that the research summary contains all necessary elements.

Standard Research Summary

Purpose of the Study

Objectives & hypotheses to be tested

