This study is being conducted to assess the utility of hyperbaric oxygen as an adjunctive treatment to reduce postoperative complications. It is hypothesized that ${\rm HBO}_2$ given in the immediate postoperative period will reduce postoperative complications in patients undegoing below-the-knee amputations. The objective of this study will be to compare treatment and standard care groups, randomly created of eligible patients, to compare their postoperative complications and to assess their postoperative hospital length of stay, 90-day mortality, failure to heal at 4 and 8 week follow-up visits and ability to ambulate with a prosthesis at 6 months post amputation.

Background & Significance

• Should support the scientific aims of the research

Lower limb amputations (LLA) are commonly performed at Duke University Hospital and are associated with major morbidity, mortality, hospital length of stay and costs. We are proposing a clinical study to test whether hyperbaric oxygen therapy (${\rm HBO}_2$) administered immediately after surgery for ten 2 hour treatments following below knee amputation (BKA) in diabetic patients will reduce surgical site infections (SSIs), reoperations and hospital length of stay (LOS).

LLAs have major morbidity and mortality. Overall, more than 60% of patients who require LLA are diabetic¹. Wound complications occur in 12%, and reoperations in 10-16%, often for infection^{1,2}. Nearly 5% of BKAs require revision to a higher amputation level². Duke University Vascular Quality Initiative (VQI) data indicates that of the 98 LLAs performed at Duke last year 27 resulted in complications, of which 25 needed reoperation. Surgical complications after amputations result in roughly doubling of the cost incurred by hospitals³, thus less than one third of amputations incur almost half of the total cost of amputations.

Both wound healing⁴ and infection risk⁵ are related to the partial pressure of oxygen (PO_2), in affected tissues. Higher peri-wound PO_2 stimulates wound angiogenesis^{6,7} and decreases infection rate⁸. In patients requiring LLA, decreased blood flow due to diabetic microvascular disease and large vessel disease contributes to tissue hypoxia. In this population the combination of hyperglycemia and low tissue PO_2 is the major reason for both poor wound healing and surgical site infection (SSI).

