After informed consent is obtained, patients will be assigned to either a treatment group or a standard care group. Because of the nature of the treatment blinding is not possible. Patients will be informed of their group assignement when they arrive on the floor after surgery. Each patient in the treatment group will receive ${\rm HBO}_2$ treatments in the Duke Center for Hyperbaric Medicine and Environmental Physiology using normal treatment protocols already established and approved by DUHS for the administration of HBO $_2$. Treatments will be given twice per day until the patient is discharged or 10 treatments are given.

Treatments will consist of breathing 100% O $_2$ through a head tent while inside a hyperbaric chamber at 2 ATA for 2 hours. Hyperbaric chambers at Duke allow for the presence of nursing staff and emergency access into the chamber while treatment is ongoing. Patients will experience a 15 minute compression and 5 minute decompression phase.

The Vascular Quality Initiative (VQI) is a multicenter voluntary reporting system for outcomes related to vascular surgery. The primary outcome of this study, postoperative complications, will be those outcomes meeting the definition set out in the VQI data dictionary, the set of definitions for inclusion in the VQI databse. This allows for a standard definition of complications recognized by a majority of academic medical centers across the country.

Secondary outcomes will include: Hospital length of stay, 90-day mortality, failure to heal at 4 and 8 week follow-up visits and ability to ambulate with a prosthesis at 6 months post amputation. Patients will be examined daily during their inpatient stay and then at 4 and 8 week follow-up visits once discharged from the hospital. Periwound transcutaneous oxygen presures will be taken prior to administration of HBO₂ and at the completion of 10 treamtents.

The statistical plan for this study will test non-directional hypotheses (two-sided tests). Bonferroni correction will be used to adjust for multiple tests. SAS 9.4 (SAS Institute, Inc.) will be used to analyze the data. The main analysis of the primary efficacy hypotheses will include data from all randomized patients in the group to which random assignment is made. Hence, the analysis will be intention to treat, and regardless of subsequent events and every effort will be made to continue to follow all patients that begin the study.

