Proportions and differences in proportions in the difference complication rate requiring reoperation in 30 days will be estimated along with 95% confidence interval. The difference in reoperation rates will be examined using Z-test. The analysis is similar for secondary outcomes. Exploratory outcome of 90-day mortality in the two treatment groups will be determined using Kaplan-Meier techniques with log-rank test. The Cox proportional hazards model will be used to determine the predictors of survival. Model assumptions will be examined and goodness of fit of these models will be assessed.

Because studies of this type have not been conducted before an effect size is difficult to estimate. However, based treatment of diabetic foot ulcers with HBO2¹ it is hoped that an effect size of 0.62, or reduction of complications by 60% can be seen. 80% power will be acheived by randomizing 40 subjects into each of the treatment and standard care groups. Hence, 80 subjects will be needed for this study. Given the high volume of operations conducted at Duke this should be achievable in less than 3 years. Midpoint analysis may produce results even sooner than that.

Selection of Subjects

• List inclusion/exclusion criteria and how subjects will be identified.

The subject selection will be equitable and all relevant demographic groups will have access to study participation (per 45CFR46.111(a)(3), 21CFR56.111(a)(3)).

Inclusion Criteria

- 1. Patients over the age of 18
- 2. Able to Consent
- 3. Have been identified as having a non-traumatic indication for amputation surgery of lower limb
- 4. Be cleared and scheduled for surgery for below-knee amputation of lower limb at Duke University Hospital
- 5. Be able to receive HBO₂ therapy.

Exclusion Criteria

- 1. Unable to consent
- 2. Unable to receive hyperbaric oxygen
- 3. No longer need to receive surgery for amputation of lower limb
- 4. Patients with End Stage Renal Disease on dialysis
- 5. Patients with current renal failure as measured by creatinine levels vs baseline change of more than 1 mg/dL and for whom dialysis is expected to be required within the next month
- 6. Patients with Calciphylaxis
- 7. Patients with traumatic injuries that are the cause of the amputation

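### The declared primary outcome is all VQI-defined complications, but the analysis text estimates and tests complications requiring reoperation in 30 days

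*Combined protocol and SAP*

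**What the plan says.** The primary objective (Research Summary) is to "assess whether patients receving treatment suffered fewer complications, as defined by the Vascular Quality Initiative". The hypothesis under Purpose of the Study is that hyperbaric oxygen "given in the immediate postoperative period will reduce postoperative complications in patients undegoing below-the-knee amputations". Design & Procedures states: "The primary outcome of this study, postoperative complications, will be those outcomes meeting the definition set out in the VQI data dictionary". None of these limits the outcome to reoperated cases or gives a window. Both power statements (Design & Procedures; Data Analysis & Statistical Considerations) also speak of a 60% reduction of complications.

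The analysis text appears in both of those sections with the same wording. It opens with the intention-to-treat statement, "The main analysis of the primary efficacy hypotheses will include data from all randomized patients", and continues: "Proportions and differences in proportions in the difference complication rate requiring reoperation in 30 days will be estimated along with 95% confidence interval". The next sentence applies a Z-test to reoperation rates, and the one after says secondary outcomes are analysed in a similar way. No sentence gives an analysis of all VQI-defined complications.

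The secondary list begins "Secondary outcomes will include: Hospital length of stay, 90-day mortality, failure to heal at 4 and 8 week follow-up visits" and ends with ambulation on a prosthesis at 6 months. Reoperation is not on it.

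Background & Significance counts the two outcomes separately: "98 LLAs performed at Duke last year 27 resulted in complications, of which 25 needed reoperation". It also names reoperations, with surgical site infections and length of stay, among the things the treatment is meant to reduce.

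**The concern.** An analyst cannot follow both texts. If the analysis text governs, complications managed without reoperation, and those reoperated after day 30, drop out of the only specified estimate and test. If the outcome paragraph governs, the declared primary outcome has no analysis sentence of its own.

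The contradiction also leaves room to choose. One endpoint is called primary and the other stands where the primary analysis should be, so either could be reported as the planned result. Treatment is open ("Because of the nature of the treatment blinding is not possible"), so staff can see outcomes by arm as they accrue, and the sample-size paragraph mentions a possible midpoint analysis. Bonferroni correction is planned, but the number of tests is not given. It would cover both tests if both were declared; it cannot correct an undisclosed choice between them.

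**Working it through.** **1. Which endpoint each place names**

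| Place | Endpoint | Window |
|---|---|---|
| Primary objective | VQI-defined complications | none |
| Hypothesis (Purpose of the Study) | postoperative complications | none |
| Outcome paragraph (Design & Procedures) | VQI-defined complications | none |
| Estimate (both copies of the analysis text) | complications requiring reoperation | 30 days |
| Z-test (both copies) | reoperation rates | not repeated |
| Power statements (both copies) | complications | none |
| Secondary outcomes | reoperation not listed | – |

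Two consecutive sentences name reoperation, and both are repeated in the second section, so this is not one slip of the pen. The Z-test suits either binary endpoint; only the endpoint is in conflict.

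**2. The plan's own sample size**

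Reading 0.62 as a standardized effect, with two-sided alpha 0.05 (assumed; the documents give no number), n per arm = 2(1.96 + 0.84)²/0.62² ≈ 40.8, so 41. Power at 40 per arm is 79.2%. The stated 40 therefore reproduces, but the calculation uses no event rate and cannot show which endpoint was meant.

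**3. Size of the gap on the local data**

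Complications: 27/98 = 27.6%. Reoperated complications: 25/98 = 25.5%. Outside the narrower endpoint: 2/27 = 7.4% of complications.

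Assumptions for an illustration: 40 per arm; control complication rate 27/98 = 0.2755; treated rate either the same or 0.4 × 0.2755 = 0.1102; each complication reoperated with probability 25/27 in both arms; every reoperation within 30 days.

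Expected complications left out of the specified test, among 80 patients:
- no effect: 40 × (0.2755 + 0.2755) × 2/27 = 1.63
- 60% reduction: 40 × (0.2755 + 0.1102) × 2/27 = 1.14

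The chance that at least one is left out is 1 − (1 − p_C × 2/27)^40 × (1 − p_T × 2/27)^40, where p_C and p_T are the control and treated complication rates. This gives 80.8% and 68.4%.

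**4. How often the choice changes the result**

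Exact enumeration of all outcomes, with complications binomial in each arm and reoperations binomial given complications. Pooled two-sided test: z = (difference in proportions)/√(p̄(1 − p̄) × 2/40), rejecting at |z| ≥ 1.96.

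| | No effect | 60% reduction |
|---|---|---|
| Complications test significant | 4.92% | 47.9% |
| Reoperation test significant | 4.99% | 44.5% |
| Tests disagree | 2.77% | 9.15% |

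With no effect, both tests are significant in 3.57% of trials, so at least one is in 4.92 + 4.99 − 3.57 = 6.34%. That is the type I error if the significant test is picked without disclosure. With both declared and tested at 0.025 each, it is 3.13%.

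**5. Range for the unknown share**

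The documents do not say how many local reoperations fell within 30 days, so the share is varied by assumption.

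| Share reoperated within 30 days | Disagree, no effect | Disagree, 60% reduction | Type I error, undisclosed choice |
|---|---|---|---|
| 25/27 (93%) | 2.8% | 9.1% | 6.3% |
| 75% | 5.3% | 20.1% | 7.6% |
| 50% | 7.5% | 31.0% | 8.9% |

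**The case against.** Only one outcome is ever called primary, and no sentence calls reoperation primary. That reading rests on position within a loosely written paragraph. Its first sentence is garbled and still says complication rate, and the paragraph labels 90-day mortality exploratory although the outcome list makes it secondary. The VQI dictionary is not in the documents and may carry its own window or a reoperation criterion. The local figures cover all lower-limb amputations, not the eligible below-knee population, and on those figures only one or two of 80 patients are affected.

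Part of this stands. The drafting is poor enough that intent cannot be inferred from it, what the dictionary says about timing cannot be checked here, and the figures are illustrations. Post-hoc choice of an endpoint is also possible in a blinded trial; open treatment makes it easier but is not the root of the problem.

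The contradiction survives. The sentence extending the analysis to secondary outcomes implies that what precedes it is the primary analysis. A window inside the dictionary would not turn a test of reoperation into a test of complications, since the protocol's own background counts the two separately. The background's mention of reoperations as a treatment target makes reoperation a genuine rival endpoint, which strengthens the case for settling the matter.

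**Conclusion.** The concern holds and must be fixed. As written, the specified estimate and Z-test are not of the declared primary outcome, and the endpoint they use is on no outcome list. The severity rests on that contradiction, not on the arithmetic. At the local share of 25/27, about 1 to 2 complications in 80 patients fall outside the test, and an undisclosed choice costs about 1.3 percentage points of type I error (6.3% against 5.0%). This assumes two-sided alpha 0.05, local rates for all lower-limb amputations, the same reoperation share in both arms, and all local reoperations within 30 days. The last assumption favours the plan: at an assumed share of 50% the choice raises type I error to 8.9%. The power figures of 44.5% and 47.9% differ little between endpoints; their shortfall from 80% is a separate sample-size matter and adds no weight here.

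**What to change.** Before any comparative results are seen, including at a midpoint analysis, name one primary endpoint with a window confirmed by the sponsor. Use it in the primary objective, the hypothesis, the background statement of what is tested, the outcome paragraph, and both copies of the analysis text and power statement.

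Wording that matches the stated objective: *The primary outcome is any VQI-defined postoperative complication within [window confirmed by the sponsor] of amputation, compared between arms by the difference in proportions with 95% CI and a two-sided Z-test in all randomized patients. Complication requiring reoperation within 30 days is a secondary outcome.*

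Alternatively, declare complication requiring reoperation within 30 days as primary, change the objective, hypothesis, outcome definition and power statement to match, and list all VQI-defined complications as secondary.

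The cost is a wording amendment, plus confirmation that the trial data capture the chosen window and the date of any reoperation. The background gives no timing for the local reoperations, so a 30-day count cannot be assumed to be available already.

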Hyperbaric oxygen (HBO $_2$) can increase wound PO $_2$ to supranormal levels even in the presence of peripheral vascular disease 9 . Evidence suggests that HBO $_2$ can facilitate healing in chronic diabetic foot ulcers 10,11 . A retrospective analysis suggests that perioperative HBO $_2$ may prevent postoperative neurosurgical infections 12 . Regarding postop SSIs and perioperative high inspired O $_2$, although there has been some inconsistency in the published data 13 , well-executed studies have supported the notion that high-inspired O $_2$ during anesthesia may prevent SSIs 14,15 . Hyperbaric oxygen specifically has been shown to be effective in the treatment of sternal infection, a classic complication of a poorly perfused surgical wound, and osteomyelitis after cardiothoracic surgery 16 . A double blind placebo controlled trial has showed the efficacy of HBO $_2$ as an adjunct to managing crush injuries of the limbs 17 .

Recently concern has been raised about some adverse consequences of perioperative hyperoxia, including increased respiratory complications and mortality ¹⁸. However, a Cochrane systematic review from 2015 reported no statistically significant effect of intraoperative oxygen concentration on all-cause mortality ¹³. However, possible beneficial effects of hyperoxia are likely to be minimal when the focus is on the intraoperative phase, when an anesthesia provider is continuously providing careful management of blood pressure, blood glucose and administering fluid therapy. We feel, and studies cited above have shown, that the greatest beneficial impact of hyperoxia is likely to be after surgery, when the processes of healing and host response to bacterial infection occur over several days or weeks. Hence, the proposed intervention is intended to maximize the demonstrated beneficial physiological effects of hyperoxia by inducing it in the postoperative period.

Citations:

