The statistical plan for this study will test non-directional hypotheses (two-sided tests). Bonferroni correction will be used to adjust for multiple tests. SAS 9.4 (SAS Institute, Inc.) will be used to analyze the data. The main analysis of the primary efficacy hypotheses will include data from all randomized patients in the group to which random assignment is made. Hence, the analysis will be intention to treat, and regardless of subsequent events and every effort will be made to continue to follow all patients that begin the study.

Proportions and differences in proportions in the difference complication rate requiring reoperation in 30 days will be estimated along with 95% confidence interval. The difference in reoperation rates will be examined using Z-test. The analysis is similar for secondary outcomes. Exploratory outcome of 90-day mortality in the two treatment groups will be determined using Kaplan-Meier techniques with log-rank test. The Cox proportional hazards model will be used to determine the predictors of survival. Model assumptions will be examined and goodness of fit of these models will be assessed.

Based on randomized control trials of ${\rm HBO}_2$ effects on healing diabetic foot ulcers this study is proposed to achieve 80% power to detect an effect size of 0.62, or reduction of complications by 60% by randomizing 40 subjects into each of the treatment and placebo groups. Hence, 80 subjects will be needed for this study. Given the high volume of operations conducted at Duke this should be achievable in less than 3 years.	
Data & Safety Monitoring	
 Summarize safety concerns, and describe the methods to monitor research subjects and their data to ensure their safety, including who will monitor the data, and the frequency of such monitoring. If a data monitoring committee will be used, describe its operation, including stopping rules and frequency of review, and if it is independent of the sponsor (per 45 CFR 46.111(a) (6)). Clinical and demographic data will be collected electronically and stored using Duke University's Redcap system. Information pertaining to blinding, patient treatment, or any other study information that may arise incidentally will be stored in the Duke hyperbaric treatment facility in a locked cabinet in the nurse manager's office. 	
Privacy, Data Storage & Confidentiality	
Complete the Privacy and Confidentiality section of the iRIS submission form.	
Study Scope	

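### The 30-day reoperation rate scores death without reoperation as a non-event, and no rule says how death is scored for healing or ambulation

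*Combined protocol and SAP*

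**What the plan says.** The statistical text appears twice in the Combined protocol and SAP, under Design & Procedures and under Data Analysis & Statistical Considerations.

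- **Quantity estimated:** the "complication rate requiring reoperation in 30 days will be estimated along with 95% confidence interval".
- **Test:** "The difference in reoperation rates will be examined using Z-test".
- **Who is analysed:** the main analysis "will include data from all randomized patients in the group to which random assignment is made"; both sections add that "the analysis will be intention to treat, and regardless of subsequent events".
- **Named primary outcome:** Design & Procedures defines postoperative complications by reference; they "will be those outcomes meeting the definition set out in the VQI data dictionary". The components are not listed, so the documents do not show whether death is one of them.
- **Secondary outcomes:** these include "failure to heal at 4 and 8 week follow-up visits and ability to ambulate with a prosthesis at 6 months post amputation". They are to be analysed in a similar way, and nothing is said about patients who die before the visit.
- **Mortality:** 90-day mortality is compared by Kaplan-Meier and log-rank. The statistical text calls it exploratory; the secondary objectives list it as secondary.
- **Background:** Background & Significance describes amputation as carrying major mortality and reports concern about "some adverse consequences of perioperative hyperoxia, including increased respiratory complications and mortality". It then cites a systematic review that found no significant effect of intraoperative oxygen concentration on all-cause mortality.

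**The concern.** A reoperation proportion over all randomized patients has two states: reoperated by day 30, or not. A patient who dies on day 5 without returning to theatre falls in the second state, together with patients whose stump healed. The protocol does not choose this rule. It follows from the endpoint and the denominator.

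If early mortality were the same in both arms, this would matter little. If the treated arm had more early deaths, fewer of its patients would remain at risk of reoperation and its observed rate would fall. Part of a harm could then read as benefit. The protocol itself raises mortality as a possible consequence of hyperoxia, so the possibility cannot be set aside in advance.

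For healing and ambulation the difficulty is that the scoring is left open. Depending on the choice made at analysis, the dead could be counted as failures, counted as non-failures or left out, and these choices can give different answers.

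**Working it through.** **Inputs from the documents.** Reoperation rate r = 25/98 = 25.5% (Background & Significance; all lower limb amputations in one year at the centre). Sample size is 40 per arm. Tests are two-sided. The hoped-for reduction is 60%, which at this rate is 0.60 × 25.5 = 15.3 points, or 10.2 versus 4.1 expected reoperations per 40.

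**Assumed.** Alpha is taken as 0.05 from the 95% interval; the number of tests for Bonferroni is not given. All death rates are illustrative.

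The plan has no figure of its own on deaths to reproduce. Its 40 per arm is approximately recovered when 0.62 is read as a standardized effect (41 per arm; 79.2% power at 40), but nothing below depends on that.

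**Step 1: bias with no true effect on reoperation.** Let d be the risk of dying before any reoperation, and r the risk of reoperation otherwise, equal in both arms.

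- Observed reoperation proportion = r(1 − d)
- Death or reoperation = r(1 − d) + d
- Shift in reoperation (HBO2 minus control) = −r(d_HBO2 − d_control)

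For deaths of 5% versus 15%:

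- Reoperation: 0.255 × 0.95 = 24.2% versus 0.255 × 0.85 = 21.7%, a shift of −2.6 points
- Death or reoperation: 29.2% versus 36.7%, a shift of +7.4 points

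**Step 2: chance of a falsely significant benefit.** With p_C and p_T the observed reoperation proportions and p̄ their mean, the normal approximation is

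Φ{[(p_C − p_T) − 1.96√(2p̄(1 − p̄)/40)] / √([p_C(1 − p_C) + p_T(1 − p_T)]/40)}.

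For 5% versus 15%: (0.0255 − 1.96 × 0.0940)/0.0940 = −1.69, which gives 4.6%.

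| Assumed deaths, control vs HBO2 | Shift in reoperation (points) | Shift in death or reoperation (points) | Chance of false benefit |
|---|---|---|---|
| 5% vs 5% | 0 | 0 | 2.5% |
| 5% vs 10% | −1.3 | +3.7 | 3.4% |
| 5% vs 15% | −2.6 | +7.4 | 4.6% |
| 5% vs 20% | −3.8 | +11.2 | 6.1% |
| 10% vs 30% | −5.1 | +14.9 | 8.1% |

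**Step 3: healing and ambulation.** Assume deaths of 10% versus 20% and no true effect among survivors.

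- Failure to heal, 30% among survivors: 27% versus 24% if the dead are not counted as failures; 37% versus 44% if they are.
- Ambulation, 50% among survivors: 45% versus 40% over all randomized, because the dead do not walk; 50% versus 50% if the dead are dropped.

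**Step 4: power if the composite replaced the endpoint.** Assume a true 60% reduction in reoperation and equal deaths, 40 per arm.

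- 5% deaths: reoperation 24.2% versus 9.7%, power 41%; composite 29.2% versus 14.7%, power 35%.
- 10% deaths: reoperation 23.0% versus 9.2%, power 39%; composite 33.0% versus 19.2%, power 29%.

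**The case against.** **Deaths will be seen anyway.** The trial compares 90-day mortality by arm, so an excess would be reported. That stands. But nothing connects that comparison to the reading of the reoperation result, and a log-rank test in 80 patients has little power to detect an excess.

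**The primary outcome may already include death.** If the registry's complication definition covers death, the named outcome would be free of this problem. The documents do not settle it. The quantity actually tested is reoperation, so the gap in the Z-test remains either way.

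**The mortality signal is thin.** The protocol answers its own concern with a review showing no significant effect, and by its title the source of the concern is a long-term follow-up after abdominal surgery. That is fair: the documents do not show that early deaths will differ, and this point does not claim they will.

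**Stronger readings that do not hold.** A reader might infer three things.

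- *That the plan deliberately classes deaths as successes.* It does not say so; the scoring results from silence.
- *That ambulation has the same flaw.* It does not. In an all-randomized proportion, "ability to ambulate with a prosthesis at 6 months post amputation" counts a death as a failure, which penalizes the arm with more deaths. The risk there is that the dead are dropped, leaving a survivors-only comparison.
- *That deaths alone could produce a significant result.* Take 4 versus 11 reoperations (p = 0.045) becoming 8 versus 12 events once 4 versus 1 deaths are added (p = 0.30). Here the 7-patient gap is assumed. Three extra deaths would hide only about 3 × 25/98 = 0.77 reoperations. Most of the change in p comes from asking a different question.

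**Conclusion.** The point holds in a limited form. As written, the 30-day reoperation comparison scores death without reoperation as a non-event, and the handling of death is unstated for healing and ambulation.

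The resulting bias is modest: about 2.6 points for an assumed 10-point excess of deaths, against the 15.3-point reduction the trial hopes to see. It is zero if early mortality is equal. These sizes rest on the 25/98 rate carrying over to trial patients, on assumed death rates, and on deaths being unrelated to a patient's underlying risk of reoperation.

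The case for acting rests on direction. In the unequal-mortality scenarios above, reoperation alone points toward benefit while death or reoperation points toward harm, and the plan has no step that would bring the two together before a conclusion is drawn.

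**What to change.** 1. State that a death without reoperation is a non-event in the 30-day reoperation proportion, so that the rule is explicit.
2. Pre-specify a companion analysis of death from any cause or reoperation within 30 days, in all randomized patients, with the same Z-test and 95% confidence interval. Require it to agree in direction with the reoperation result before benefit is claimed. As a condition rather than a second route to a positive finding, it needs no share of the Bonferroni adjustment.
3. Report reoperations and deaths by arm beside both analyses.
4. For healing at 4 and 8 weeks and ambulation at 6 months, count death before the assessment as failure rather than leaving those patients out.

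**Cost.** The change is mostly wording. Deaths to 90 days are already needed for the mortality comparison; vital status at 6 months must be confirmed for ambulation. Deaths unrelated to the stump will add noise to the composite. Making the composite the primary endpoint is optional: at 5–10% mortality it would lower power at 40 per arm by about 6 to 10 points (41% to 35%, or 39% to 29%).
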